10.4.1. Subject Characteristics

A disposition table will be presented to show the number and percentage of subjects in each population set, study completers, and early discontinuations along with reasons for discontinuation.

Baseline characteristics will be summarized for the Safety Population and the Full Analysis Set.

10.4.2. Efficacy Analyses

Efficacy endpoints will be assessed using the FAS. Continuous monitoring will be performed with respect to the number of subjects evaluable for the primary endpoint. When the required number of subjects with positive ¹⁸F-DCFPyL PET/CT scans and information for the composite truth standard are available for calculation of the CLR, subject enrollment and follow-up assessments will conclude, and the study database will be locked for analysis. Any subjects who are undergoing efficacy evaluations who have not contributed endpoint data at the time of database lock will be censored and will be treated as unevaluable for efficacy.

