If evaluable histopathology is not available and conventional imaging of the PyL-suspected lesion(s) is not informative, those subjects who are planned to receive locoregional RT without concomitant androgen deprivation therapy (ADT) within 60 days following PyL PET/CT imaging will continue on-study and be followed for PSA changes following RT alone. PSA (total) will be collected every 3 months post-RT alone (until Response is achieved as defined in [Section 8.1](#), for a maximum of up to 9 months total duration) and sent to the central lab for analysis. All other subjects not initiated on locoregional RT alone within 60 days post PyL PET/CT imaging will be discontinued from the study.

Subjects who are initiated on any systemic therapy for prostate cancer (PC) will be discontinued from the study.

[figure not shown]
Once the study reaches the required number of subjects evaluable for calculation of the primary endpoint as described in [Section 10.4.2](#), subject enrollment and follow-up assessments will conclude, and the study database will be locked for analysis. Adverse events (AEs) will be assessed following ¹⁸F-DCFPyL dosing (Day 1), and again via a safety phone call 7 (±3) days post-¹⁸F-DCFPyL dosing to capture any late-occurring AEs.

Medical Management Questionnaires (MMQs) will be completed by the treating investigator at two time-points during the study to capture intended changes in the clinical management for all subjects who underwent ¹⁸F-DCFPyL PET/CT imaging:

- **Prior to ¹⁸F-DCFPyL dosing**, the treating investigator will complete the Pre-PyL MMQ based on baseline clinical information and results from conventional imaging.
- **Post-¹⁸F-DCFPyL imaging**, the treating investigator will complete the Post-PyL MMQ based on the additional result from local interpretation of the ¹⁸F-DCFPyL PET/CT scan, to assess whether an intended change to the initial medical management plan is warranted due to the PyL finding.

See [Figure 1](#) and [Table 3](#) for the study schema and schedule of study assessments. Details on study procedures for each visit are described in [Section 4.3](#).

Figure 1: Study Schema

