If an evaluable histopathology result for prostate cancer is not available and follow-up conventional imaging of the PyL-suspected lesion is not informative, subjects initiated on locoregional RT alone (no concomitant ADT) within 60 days following PyL PET/CT imaging will be followed every 3 months (± 7 days) for up to an additional 9 months to assess PSA response to RT alone (without concomitant ADT administered during this time). To be evaluable for PSA response, applicable subjects should undergo RT with fields and target volumes adjusted based on presence of PyL-positive prostate bed, pelvic nodal, visceral or limited osseous metastases.

A blood draw for PSA (total) will be obtained and sent to the central lab at each follow-up assessment. PSA response is defined by decline of $\geq 50\%$ from baseline PSA and must be confirmed within 4 weeks. Subjects will complete follow-up within the 9-month duration once PSA response is confirmed per the central lab.

Concomitant medications and procedures will be collected. See [Section 8](#) Assessment of Efficacy.

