4.4. Study Duration

Subjects will be deemed enrolled once they sign informed consent and meet all inclusion and no exclusion criteria and complete all screening assessments. The study duration of subject participation from Screening through ¹⁸F-DCFPyL PET/CT imaging and Efficacy visit(s), if applicable, will be a maximum duration of approximately 12 months. At a minimum, all subjects who receive a dose of ¹⁸F-DCFPyL will be followed from time of informed consent until the safety phone call on Day 8 (± 3).

Only subjects with positive PyL PET/CT scans (detection of disease at any site) will be followed at the Efficacy visit(s). Subjects will undergo Efficacy assessments based on the site's local PyL PET/CT interpretation and clinical presentation.

- Subjects with any positive PyL PET/CT finding(s) per local interpretation will be evaluated as described in [Section 4.3.5](#).
- Subjects without any positive PyL PET/CT finding per local interpretation will complete the study through the safety phone call; no further visits will be required.

The Sponsor may conclude the study before subjects complete their efficacy follow-up assessments (see [Section 10.4.2](#))

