6.2. Concomitant Medications and Procedures

All concomitant medications and medical procedures will be recorded in the eCRF from post-¹⁸F-DCFPyL dosing (Day 1) and at all subsequent study visits as shown in [Table 3](#) Schedule of Assessments.

Any new or changed medications, including prostate cancer therapy, from time of ¹⁸F-DCFPyL injection to each study visit must be recorded in the eCRF. Subjects who receive concomitant systemic or investigational therapy for prostate cancer anytime during participation in the study will be discontinued from the study.

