PSA response following	No observed $\geq 50\%$	N/A	FP
locoregional RT	decrease from		
	baseline up to 9		
	months from start of		
	RT, but PSA results		
	are available		

N/A: not applicable

Lesion mismatches are defined as False Positives due to the subject having a positive finding (by Central PyL read) on the PyL scan.

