8.6.4. Laboratory Data

Only serum PSA will be assessed in this study. No other laboratory parameters are required. PSA will be an analyzed by a central laboratory. The baseline value is required for all subjects in the safety population and will be presented as descriptive statistics. For those subjects undergoing efficacy follow-up who will undergo radiation therapy, PSA will be evaluated every three months until the baseline value decreases by at least 50%, or until the subject is followed for nine months. For those subjects, the PSA values and changes from baseline will be summarized at each post-treatment visit. The number and percent of subjects who achieve the 50% reduction from baseline at each 3-month follow-up visit will be presented as an efficacy endpoint.

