9.1.4. Visit Windows

The visit windows for each study visit are detailed in Table 7.

Table 7: Visit Windows (Days)

Visit	Relative Target Day	Visit Window (Day)
Screening	-30 to 1	-30 to 1
Study drug dosing and Imaging	1	1
Safety phone call	8	5 to 11
Efficacy follow-up (surgery, biopsy or conventional imaging)	2 to 60	2 to 60
PSA month 3 (locoregional RT)	3 months ±7 days after start of RT, which can be on days 2 to 60	85 to 157
PSA month 6 (locoregional RT)	6 months ±7 days after start of RT, which can be on days 2 to 60	115 to 187
PSA month 9 (locoregional RT)	9 months ±7 days after start of RT, which can be on days 2 to 60	145 to 217

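### SAP Table 7: the month-6 and month-9 PSA windows contradict their own targets; a smaller point is that Table 4 does not say how much follow-up a PSA false positive needs

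*Protocol*

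**What the plan says.** **Visit windows.** SAP 9.1.4, Table 7, gives three PSA visits after locoregional RT, at 3, 6 and 9 months. Each has a tolerance of 7 days and an RT start on Days 2 to 60; the last target reads "9 months ±7 days after start of RT, which can be on days 2 to 60". The printed windows are Days 85 to 157, 115 to 187 and 145 to 217. SAP 8.6.4 uses these visits: the number and percent of subjects who "achieve the 50% reduction from baseline at each 3-month follow-up visit will be presented as an efficacy endpoint".

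**PSA false positive.** SAP 5.1.1, Table 4, classes a PSA-route subject as FP if no fall of at least 50% is observed up to 9 months from the start of RT. It then adds "RT, but PSA results" are available. The FP bullets in protocol 10.4.2.1 and SAP 5.1.1 also say up to 9 months, for RT without concomitant ADT. None of the three states a minimum number of samples or a last visit.

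**End of follow-up.** Protocol 4.3.5.1 says "Subjects will complete follow-up within the 9-month duration once PSA response is confirmed per the central lab". Protocol 4.4 says "The Sponsor may conclude the study before subjects complete their efficacy follow-up assessments". Protocol 10.4.2 says "Any subjects who are undergoing efficacy evaluations who have not contributed endpoint data at the time of database lock will be censored" and treated as unevaluable for efficacy. Protocol 4.1 adds "Subjects who are initiated on any systemic therapy for prostate cancer (PC) will be discontinued from the study", and protocol 6.2 has a similar rule.

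**The concern.** The Table 7 windows rise by 30 days per row while their targets rise by 90. If they are programmed as printed, month-6 results will be filed mostly under month 9 or lost, and true month-9 results will be lost altogether. The summary at stake is one that the SAP itself calls an efficacy endpoint.

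The second issue is a gap in a definition. Take a subject with one PSA at month 3, no 50% fall, and database lock at month 5. Read literally, Table 4 makes him FP: no fall was seen and PSA results exist. Under protocol 10.4.2 he is unevaluable, unless one early PSA counts as endpoint data, which is not defined. Two programmers could code him differently. CLR = TP/(TP+FP), so the choice changes the denominator.

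The two readings push in opposite directions. If pending subjects are unevaluable, responders can be classified soon after month 3 and non-responders only at month 9, which tends to raise the CLR. If partly followed subjects are FP, the CLR falls.

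**Working it through.** **1. Table 7.** Inputs, all from the table: RT start on Days 2 to 60, targets of 3, 6 and 9 months, tolerance of 7 days. Window = (2 + 30m − 7) to (60 + 30m + 7) for month m.

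| Visit | Computed | Printed |
|---|---|---|
| Month 3 | 2+90−7 = 85 to 60+90+7 = 157 | 85 to 157 |
| Month 6 | 2+180−7 = 175 to 60+180+7 = 247 | 115 to 187 |
| Month 9 | 2+270−7 = 265 to 60+270+7 = 337 | 145 to 217 |

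Month 3 reproduces exactly, so the SAP uses a 30-day month. The printed month-6 window is RT start + 120 days (4 months) and the printed month-9 window is RT start + 150 days (5 months). Months of 30.33 to 30.44 days do not rescue it: they give about 177–178 to 249–250 and 268–269 to 340–341.

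**2. Where on-target samples land.** For each RT start day s from 2 to 60 (59 days), I compared s + 30m with the three printed windows.

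- Month 9: Days 272 to 330. The last window closes on Day 217, so 0 of 59 fall in any window. Using the full ±7 days does not help, since the earliest on-schedule day is 265.
- Month 6: Days 182 to 240. In its own window for s = 2–7 (6 of 59, where it is also in the month-9 window); only in the month-9 window for s = 8–37 (30 of 59); in none for s = 38–60 (23 of 59).
- Month 3: always in its own window, but also in a later one for s = 25–60 (36 of 59).

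**3. Threshold.** Success needs a lower 95% bound above 0.2 for at least two of three readers (SAP 8.5.2.1). Wald bound: p − 1.96·√(p(1−p)/n). The plan is sized at n = 81 (1.96² × 0.3 × 0.7 / 0.1² = 80.67). The TP counts below are chosen to sit near the threshold and refer to one reader.

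| TP/n | Lower bound | Result |
|---|---|---|
| 25/81 | 0.2080 | pass |
| 24/81 | 0.1969 | fail |
| 24/79 | 0.2024 | pass |
| 25/83 | 0.2025 | pass |
| 25/84 | 0.1998 | fail |

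With 24 TP, moving two partly followed subjects from FP to unevaluable turns a fail into a pass. With 25 TP, counting three more FP beyond 81 turns a pass into a fail.

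**4. Average size.** The documents give neither the PSA-route share nor accrual, so I assumed them: accrual over 12 or 24 months; PSA route 5% or 20% of evaluable subjects; true CLR 30% on every route; RT start 0–2 months after the scan; responses at months 3/6/9 in 50/30/20%, 80/15/5% or equal thirds; 192 scans, 60% positive, 70% of those evaluable, lock at the 81st evaluable subject. Simulated overall CLR is 30.1–31.7% if pending subjects are unevaluable and 28.2–30.1% if partly followed subjects are FP. The expected evaluable number is 192 × 0.6 × 0.7 = 80.6, so only about half the runs reach 81, and when the others lock is a further assumption. I use these ranges only for scale.

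**The case against.** Several stronger readings are tempting, and the documents do not support them.

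- *The window error biases the primary endpoint.* No text says that Table 7 selects PSA values for the CLR. Table 4 is worded by time from the start of RT. What is shown to be affected is the by-visit summary.
- *Unconfirmed falls count as TP.* The TP bullets in protocol 10.4.2.1 and SAP 5.1.1 omit the word confirmed, and SAP 8.6.4 stops sampling at the first 50% fall. But both TP definitions require a positive composite truth standard, which is a confirmed response (protocol 8.1, SAP 5.1.1), and Table 4 makes an unconfirmed fall unevaluable. This is wording only.
- *Subjects who start systemic therapy have no class.* The FP bullets apply to RT without concomitant ADT, so a subject who starts ADT falls outside them. Only other systemic therapy is left open.
- *PSA-route true positives are unguarded on location.* Table 4 makes RT not directed to all suspected lesions unevaluable, and protocol 4.3.5.1 ties such lesions to the local reading. A cross-reference would do.

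On the FP row itself, up to 9 months most naturally means completed follow-up, and the remark about available results may only exclude subjects with no PSA data. Early lock is an open design choice. The plan also has tipping-point deltas that are all negative, imputation by truth-standard method, and a PSA-route subgroup CLR. All this stands and makes the second point small. It does not close it, because a subject coded FP too early is neither missing nor unevaluable and so is never imputed. None of it answers the Table 7 error.

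**Conclusion.** Table 7 is wrong as written for months 6 and 9. That conclusion rests only on the table's own targets and the 30-day month that reproduces month 3. Applied as printed, it leaves every on-target month-9 result and 23 of 59 possible month-6 days untabulated, and labels another 30 of 59 as month 9 only.

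The FP follow-up requirement is a real but smaller ambiguity. One to three classifications can decide one reader's result near the threshold, but those examples use chosen TP counts, and success depends on two of three readers. Under the assumptions in step 4 the mean overall CLR moves by less than 2 percentage points either way. A reader might infer that the primary result is unsound; the documents do not show that.

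**What to change.** 1. **Table 7.** Recompute the two windows from the target column: 175 to 247 and 265 to 337 at 30 days per month. With 85 to 157 they then no longer overlap.
2. **Table 4 FP row and the SAP 5.1.1 FP bullet, with protocol 10.4.2.1 aligned.** State that a PSA-based FP requires no response with PSA follow-up through month 9. State that a subject without a confirmed response who has not reached month 9 at lock or discontinuation is unevaluable. This agrees with protocol 10.4.2 and with the restriction to RT without concomitant ADT.
3. **Optional sensitivity analysis.** Restrict the PSA route to subjects, responders and non-responders alike, for whom 9 months plus the 4-week confirmation period have elapsed by lock.
4. **Editorial.** Add the word confirmed to the two TP bullets, reconcile SAP 8.6.4 with protocol 8.1 and Table 4, and say whose lesions the RT-coverage row means.

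The cost is two table cells, a few sentences and at most one extra table from data already listed (Listings 16.2.6.9 and 16.2.8.1). The lock rule, sample size and handling of confirmed responders do not change. The wording should be settled before database lock, so that it is not chosen knowing the result.

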10.4.2.1. Primary Endpoint Analysis

The primary endpoint of the CLR is evaluated in a subset of FAS subjects with at least one positive lesion identified by PyL PET/CT imaging (per local interpretation). The CLR at the subject-level is defined as the percentage of subjects for whom there is a one-to-one correspondence between localization of at least one lesion identified on ¹⁸F-DCFPyL PET/CT imaging and the composite truth standard.

The composite truth standard is defined in [Section 8.1](#).

The CLR is computed as $100 \times TP / (TP + FP)$; TP = true positives, FP = false positives.

A true positive (TP) result is defined as a subject with both a positive lesion(s) on ¹⁸F-DCFPyL PET/CT and a positive result on the composite truth standard:

- Positive finding for prostate cancer of a PyL-suspected lesion according to local histopathology (one confirmed anatomical correlate will suffice to declare the PyL PET/CT a true positive), or
- Positive finding for prostate cancer of a PyL-suspected lesion upon follow-up conventional imaging performed following PyL PET/CT (one confirmed anatomical correlate will suffice to declare the PyL PET/CT a true positive), or
- PSA decreases drop by $\geq 50\%$ from baseline following RT without concomitant ADT up to 9 months following initiation of such treatment.

False positives will be defined as subjects with positive lesion(s) on PyL PET/CT who have the following negative findings for prostate cancer according to the composite truth standard:

- Negative finding for prostate cancer of a PyL-suspected lesion according to local histopathology, or
- Negative finding for all PyL positive lesion(s) upon follow-up conventional imaging performed following PyL PET/CT (one confirmed anatomical correlate will suffice to declare the PyL PET/CT a true positive), or
- PSA does not drop by $\geq 50\%$ from baseline following RT (without concomitant ADT) up to 9 months following initiation of such treatment.

The two-sided 95% CI for the CLR will be computed using the normal approximation to the binomial distribution. This analysis will be performed for each of the central imaging core lab

readers. If the lower bound of the 95% CI is >0.2 for two of the three independent imaging reviewers, then the primary endpoint analysis is deemed a success.

10.4.2.2. Secondary Endpoints Analyses

The secondary efficacy endpoint will be generated on the FAS for all subjects regardless of finding(s) on PyL PET/CT imaging, and be analyzed using a two-sided 95% CI presented for each imaging reviewer separately based on a normal approximation to the binomial:

- The percentage of subjects with a change in intended prostate cancer treatment plan from Pre- and Post ¹⁸F-DCFPyL PET/CT scan evaluated using a one sample binomial test. A summary of shifts in planned management from Pre- and to Post- ¹⁸F-DCFPyL imaging evaluations will also be presented.

10.4.2.3. Exploratory Endpoint Analyses

Exploratory efficacy endpoints will be generated on the FAS for detection rates on the subset of the FAS with at least one positive lesion identified by PyL PET/CT imaging for PPV and false positive scan rate endpoints.

The following endpoints will be analyzed using a two-sided 95% CI presented for each imaging reviewer separately based on a normal approximation to the binomial:

- Detection rates of ¹⁸F-DCFPyL PET/CT imaging by lesion locations (i.e., prostatic, pelvic, extra-pelvic)
- The PPV of ¹⁸F-DCFPyL PET/CT for (1) prostatic, (2) pelvic, (3) extra-pelvic regions from the composite truth standard in subjects with positive lesion(s) on ¹⁸F-DCFPyL PET/CT imaging
- The percentage of subjects with positive ¹⁸F-DCFPyL PET/CT scans who have negative findings for prostate cancer (false positive scans) based on the composite truth standard
 - The percentage of false positive scans is defined as (1-CLR)
- The detection rates of ¹⁸F-DCFPyL PET/CT imaging as a function of baseline PSA groups

10.4.3. Safety Analyses

All Safety parameters will be presented for the Safety Population.

10.4.3.1. Exposure

Volume administered of ¹⁸F-DCFPyL (mL) and activity administered (mCi) will be summarized using the Safety Population.

10.4.3.2. Treatment-Emergent Adverse Events

Treatment-emergent adverse events will be those observed from immediately post-dosing of ¹⁸F-DCFPyL on Day 1, through the safety phone call 7 (±3) days post- ¹⁸F-DCFPyL dosing for late-occurring TEAEs.

Adverse event verbatim terms will be coded using the current version of the Medical Dictionary for Regulatory Activities (MedDRA) at the start of the study. This version will be used throughout the course of the study. The frequency and percentage of subjects with an adverse event will be summarized by system organ class and preferred term. Adverse events will also be summarized by maximum severity and separately, by highest relationship to treatment.

Serious adverse events, adverse events leading to study discontinuation and adverse events leading to death will be listed.

10.4.3.3. Vital Signs

Changes in vital signs relative to ¹⁸F-DCFPyL dosing will be computed as the post-dosing values (1-2 hours post-¹⁸F-DCFPyL dosing) minus the pre-dosing value. Observed values and changes, when computed, will be tabulated for each visit using summary statistics.

10.4.3.4. Concomitant Medications and Procedures

Concomitant medications, coded using the current version of the WHO Drug dictionary at the start of the study, will be tabulated. A concomitant medication is a medication administered in the period between the day of ¹⁸F-DCFPyL dosing through the Follow-up phone call. Non-concomitant medications (those administered prior to dosing of ¹⁸F-DCFPyL) will also be tabulated and considered to be “prior” medications. Concomitant procedures are all procedures performed from the time of ¹⁸F-DCFPyL dosing until the follow-up visits are completed. Concomitant procedures will be coded using the same version of MedDRA as for medical history.

11. DIRECT ACCESS TO SOURCE DATA/DOCUMENTS

Data collected during this study may be used to support the development, registration or marketing of ¹⁸F-DCFPyL Injection. All data collected during the study will be controlled by Progenics or designee and Progenics will abide by all relevant data protection laws.

The investigator will grant monitor(s) and auditor(s) from Progenics or its designee and regulatory authority(ies) access to the subject’s original medical records for verification of data entered into the eCRF and to audit the data collection process. The subject’s confidentiality will be maintained and will not be made publicly available to the extent permitted by the applicable laws and regulations.

11.1. Study Site Monitoring

Before an investigational site can enter a patient into the study, a representative of the Sponsor will visit the investigational study site to:

- Determine the adequacy of the facilities
- Discuss with the investigator(s) and other personnel their responsibilities with regard to protocol adherence, and the responsibilities of Progenics or its representatives. This will be documented in a Clinical Study Agreement between Progenics, or designee and the investigator.

During the study, a monitor from Progenics or designee will have regular contacts with the investigational site, for the following:

- Provide information and support to the investigator(s)
- Confirm that facilities remain acceptable
- Confirm that the investigational team is adhering to the protocol, that data are being accurately recorded in the case report forms, and that investigational product accountability checks are being performed
- Perform source data verification. This includes a comparison of the data in the case report forms with the patient's medical records at the hospital or practice, and other records relevant to the study. This will require direct access to all original records for each patient (e.g., clinic charts).
- Record and report any protocol deviations not previously sent to the Sponsor, or designee.
- Confirm AEs and SAEs have been properly documented on CRFs and confirm any SAEs have been forwarded to the Sponsor, or designee, and those SAEs that met criteria for reporting have been forwarded to the IRB.

The monitor will be available between visits if the investigator(s) or other staff needs information or advice.

